6.1.1.1. Adverse device effect (ADE)

All untoward and unintended responses to the medical device.

The phrase "responses to a medical device" means that a causal relationship between the device under investigation and an AE is at least a reasonable possibility, i.e., the relationship cannot be ruled out.

All cases judged by either the reporting medically qualified professional or the sponsor as having a reasonable suspected causal relationship to the device qualifies as a device effect.

This also includes any event resulting from insufficiencies or inadequacies in the instruction for use or deployment of the device and includes any event that is a result of a user error.

All AEs will be reported from the start of epidural space localization to the end of epidural space localization.

6.1.2. Serious adverse event (SAE)

- Led to death
- Led to fetal distress, fetal death or congenital abnormality or birth defect.
- Led to serious deterioration in the health of the subject that
 - Resulted in a life-threatening illness or injury

NOTE: The term "life-threatening" in the definition of "serious" refers to an event in which the subject is at risk of death at the time of the event; it does not refer to an event which hypothetically might have caused death if it are more severe.

- Resulted in a permanent impairment of a body structure or a body function
- Required in-patient hospitalization or prolongation of existing hospitalization
- Resulted in medical or surgical intervention to prevent permanent impairment to a body structure or a body function
- Other important medical events*

*Other events that may not result in death, are not life threatening, or do not require hospitalization, may be considered a serious adverse event when, based upon appropriate medical judgement, the event may jeopardize the patient and may require medical or surgical intervention to prevent one of the outcomes listed above

To ensure no confusion or misunderstanding of the difference between the terms "serious" and "severe", which are not synonymous, the following note of clarification is provided:

The term "severe" is often used to describe the intensity (severity) of a specific event (as in mild, moderate, or severe myocardial infarction); the event itself, however, may be of relatively minor medical significance (such as severe headache). This is not the same as "serious," which is based on patient/event outcome or action criteria usually associated with events that pose a threat to a subject's life or functioning. Seriousness (not severity) serves as a guide for defining regulatory reporting obligations.

All SAEs will be reported from the start of epidural space localization to the end of epidural space localization.

6.1.2.1. Serious adverse device effects (SADE)

A serious adverse device effect (SADE) is any untoward medical occurrence seen in a patient that can be attributed wholly or partly to the device which resulted in any of the characteristics or led to a characteristics of a serious adverse event.

SADE is also any event that may have led to these consequences if suitable action had not been taken or intervention had not been made or if circumstances has been less opportune.

All cases judged by either the reporting medically qualified professional or the sponsor.

6.1.2.2. Unanticipated adverse device effect (UADE)

Any serious adverse device effect on health or safety or any life-threatening problem or death caused by, or associated with a device, if that effect, problem, or death was not previously identified in nature, severity or degree of incidence in the investigational plan or application (including a supplementary plan or application), or any other unanticipated serious problem associated with a device that related to the rights, safety or welfare of the subject.

6.1.3. Severity of adverse events

The grade refers to the severity of the AE using CTCAE Version 4.03 (published on June 14, 2010). The CTCAE displays Grade 1 to 5 with unique clinical descriptions of severity for each AE as shown in below:

Grades of AEs	Description
Grade 1	Mild; asymptomatic or mild symptoms; clinical or diagnostic observations only; intervention not indicated.
Grade 2	Moderate; minimal, local or noninvasive intervention indicated; limiting age-appropriate instrumental ADL*
Grade 3	Severe or medically significant but not immediately life-threatening hospitalization or prolongation of hospitalization indicated; disabling limiting self-care ADL**
Grade 4	Life-threatening consequences; urgent intervention indicated.
Grade 5	Death related to AE.

Table 4. Grading scales of AEs

** Self-care ADL refer to bathing, dressing and undressing, feeding self, using the toilet, taking medication, and not bedridden.

6.1.4. Associated with the use of the test device

An adverse event is considered associated with the use of the device if the attribution is certain, probably/likely, possible, or unlikely by the definitions listed as follows. The causal relationship between AEs and study device refers to WHO-UMC system for standardized case causality assessment.

Causality term	Assessment criteria*
Certain	 Event or laboratory test abnormality, with plausible time relationship to study device use Cannot be explained by disease or other medical interventions Response to withdrawal plausible (pathologically) Event definitive phenomenologically (i.e. an objective and specific medical disorder or a recognized phenomenon) Rechallenge satisfactory, if necessary
Probable / Likely	 Event or laboratory test abnormality, with reasonable time relationship to study device use Unlikely to be attributed to disease or other medical interventions Response to withdrawal clinically reasonable Rechallenge not required
Possible	 Event or laboratory test abnormality, with reasonable time relationship to study device use Could also be explained by disease or other medical interventions Information on withdrawal may be lacking or unclear
Unlikely	 Event or laboratory test abnormality, with a time to study device use that makes a relationship improbable (but not impossible) Disease or other medical interventions provide plausible explanations * All points should be reasonably conformed.

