6. ADVERSE EVENTS

6.1. Adverse Events

6.1.1. Adverse event (AE)

An AE or adverse event is:

Any untoward medical occurrence in a patient or other clinical investigation subject taking part in a trial of a medical device, which does not necessarily have to have a causal relationship with the device under investigation.

An AE can therefore be any unfavorable and unintended sign (including an abnormal laboratory finding), symptom or disease temporally associated with the use of the device, whether or not considered related to the device.

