8.5. Safety Assessment

Incidence of the adverse events will be summarized. In the case of CTCAE grade summaries, the most severe event will be presented in summary tables in the case of multiple occurrences per patient. The frequency and the percentage of each category will be presented. All safety parameters, including adverse events, adverse device effect, serious adverse event, serious adverse device effects and unanticipated adverse device effect will be listed by A and S groups. The Medical Dictionary for Regulatory Activities (MedDRA) adverse event dictionary will be used to map verbatim adverse events to preferred terms and system organ class. Fisher's exact test will be applied for comparing the incidences of adverse events between treatment groups.

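### Section 6.1.4 classes adverse events rated unlikely as device-associated and has no not-related grade, so the flag is uninformative and conflicts with the ADE test in 6.1.1.1

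*Combined protocol and SAP*

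**What the plan says.** Section 6.1.4 sets the rule: an adverse event (AE) is "considered associated with the use of the device if the attribution is certain, probably/likely, possible, or unlikely by the definitions listed as follows". The table below it defines those four grades and no others. The lowest, *unlikely*, covers an event "with a time to study device use that makes a relationship improbable (but not impossible"; its second criterion is "Disease or other medical interventions provide plausible explanations". A note to the table asks that all points of a grade be reasonably met.

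Section 6.1.1.1 defines an adverse device effect separately. The causal link between the device and "an AE is at least a reasonable possibility, i.e., the relationship cannot be ruled out". It adds that cases judged as "having a reasonable suspected causal relationship to the device qualifies as a device effect".

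Section 6.1.1 says that an AE "does not necessarily have to have a causal relationship with the device under investigation", and section 6.1.5.1 has AEs recorded whatever their attribution, with relatedness assessed for each. Events without a device link are therefore foreseen.

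For the analysis, section 8.5 states: "All safety parameters, including adverse events, adverse device effect, serious adverse event, serious adverse device effects and unanticipated adverse device effect will be listed", by group. It does not say which causality grades make an event an ADE or SADE.

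**The concern.** A causality scale is useful if it sorts events into those that may be device effects and those that probably are not. Here the dividing line lies below the lowest grade, so being graded and being associated amount to the same thing. The ADE definition draws its line elsewhere, at a reasonable possibility. An event rated *unlikely* can then be device-associated under one section and not an ADE under another.

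At stake is the interpretation of the ADE and SADE listings by group. Section 6.1.5.1 lets either a medically qualified investigator or the sponsor/manufacturer assess relatedness, so two assessors could classify the same event differently and both be following the protocol. The definition of an unanticipated adverse device effect in 6.1.2.2 also speaks of problems associated with a device, so the wide rule in 6.1.4 could be carried into that category as well.

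**Working it through.** The plan states no figure that depends on this rule, so there is none to reproduce. The check sets the wordings side by side.

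**1. Count of grades.** The rule in 6.1.4 names four grades and the table has the same four. Grades mapping to associated: 4 of 4. Without *unlikely* it would be 3 of 4.

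**2. Where each kind of event falls.**

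| Event | 6.1.4 rule | 6.1.1.1, reasonable possibility or suspicion | 6.1.1.1, gloss (link not excluded) |
|---|---|---|---|
| Certain, probable/likely, possible | associated | ADE | ADE |
| Unlikely | associated | hard to call an ADE | ADE |
| Meets none of the four definitions | not associated on a literal reading, but no grade to record it | not an ADE | not an ADE if the link is excluded |

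The second row is the conflict. The two tests within 6.1.1.1 also differ on it, so the inconsistency is partly internal to that section.

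**3. Size in symbols.** Let a be the number of AEs rated possible or stronger, u the number rated unlikely, and n the number meeting no definition.

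- Reasonable-possibility test: a device events.
- 6.1.4 rule, or the gloss: a + u.
- If assessors must choose one of the four grades and put unlinked events under *unlikely*: a + u + n.

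**4. Illustration (assumed counts, not from the documents).** Take 12 AEs with a = 3, u = 5, n = 4. The three readings give 3, 3 + 5 = 8, and 3 + 5 + 4 = 12. If u = 0 and no grade is forced, the first two readings agree and the gap is 0.

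**5. How large u is likely to be.** AEs are collected only from the start to the end of localization (Table 2 footnote, 6.1.1.1, 6.1.2). Most will coincide with device use, so the timing criterion for *unlikely* will seldom be met. An event in that window that the local anesthetic could explain fits *possible*, whose criteria allow another explanation. Hence u may be small, and removing *unlikely* from the rule would not be enough by itself: an event with a clear other cause also needs a grade of its own.

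**6. What does not depend on the rule.** The Fisher test in 8.5 is on AE incidence with no causality filter. Serious AEs go to the sponsor irrespective of relationship (6.1.5.2). The early-termination criterion in 6.2 counts dural punctures. The primary endpoint (7.1) and the 60-subject sample size (8.1) do not use causality.

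**The case against.** The strongest reply is that 6.1.4 is only a label. Relatedness is recorded for each AE together with any other suspect drug or device (6.1.5.1), ADEs have their own definition and their own listing, and no analysis in 8.5 refers to the 6.1.4 flag. The grade survives, so events can be tabulated by grade whatever the label says. The gloss in 6.1.1.1 also admits an event that is improbable but not excluded, so the clash is with part of that section only.

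Much of this stands, and it rules out several stronger readings that a reader might infer:

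- *The trial cannot separate device effects from procedural events.* The grade recorded for each AE allows a separation. Other features limit it, namely the same device in both arms and the short collection window, but they are not consequences of this rule.
- *Every AE is device-associated by construction.* The rule applies if one of four definitions is met. An AE meeting none is not literally associated; it simply has no named grade.
- *The AE and ADE categories merge.* That requires reading associated as ADE, which no passage states.
- *An air-saline difference is diluted.* The only stated safety test does not use attribution.
- *The trial's hypothesis is about safety.* Section 1 states the hypothesis as effective detection of loss of resistance; safety follows as a claimed benefit, and the objective in section 2 is efficacy.

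The reply does not remove the conflict. Section 8.5 lists ADEs and SADEs, no passage links grades to those terms, and the available wordings disagree on *unlikely* events. Nor is the wide rule a useful precaution: all AEs and serious AEs are captured regardless of attribution, so it adds no event.

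**Conclusion.** The point holds as an inconsistency in classification. All 4 available grades count as device-associated, including one defined as improbable with other plausible explanations, and no grade exists for unrelated events. This conflicts with the reasonable-possibility and reasonable-suspicion tests in 6.1.1.1 but not with that section's looser gloss. The ADE and SADE listings are therefore not uniquely defined.

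The effect is confined to device-related safety summaries. Its size equals the number of events rated unlikely, plus any unlinked events pushed into that grade for want of another. The documents give no expected AE counts, and the collection window suggests that the number rated unlikely may be low. The conclusion assumes that the four-grade table is complete as read, which is supported by the lead sentence naming the same four grades.

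**What to change.** - In 6.1.4, count an AE as device-associated (ADE, or SADE if serious) only when rated certain, probable/likely or possible. Keep *unlikely* as a recorded grade outside that set.
- Add a *not related* grade to the table and the CRF, defined by the presence of another cause and not by timing alone. Three of five grades then map to associated.
- Amend the gloss in 6.1.1.1 to match. If it stays, events rated unlikely still qualify as ADEs and the conflict remains.
- In 8.5, state this cut for ADE and SADE and tabulate all AEs by causality grade and group.

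The cost is a few sentences, one table row and one CRF box. The downside is that fewer events are labelled device-associated. No event is lost, because all AEs and serious AEs are still recorded and listed. Section 6.1.5.1 attaches a follow-up duty to ADEs, so the sponsor should check how that duty reads once the cut is stated.

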6.1.5. Reporting procedure

6.1.5.1. Adverse event (AE)

All AE's occurring during the study observed by the investigator or reported by the subject, whether or not attributed to the device under investigation will be recorded on the CRF as specified in the protocol. All ADE's will be recorded in the CRF.

The following information will be recorded: description, date of onset and end date, severity, assessment of relatedness to device, other suspect drug or device and action taken. Follow-up information should be provided as necessary.

The relationship of AEs to the device will be assessed by a medically qualified investigator or the sponsor/manufacturer and will be followed up until resolution or the event is considered stable.

All ADEs that result in a subject's withdrawal from the study or are present at the end of the study, should be followed up until a satisfactory resolution occurs.

6.1.5.2. Serious adverse reaction

As any SAE occurs, regardless of relationship with the procedure or the device, the investigational staff must inform sponsor or its delegate of their knowledge of the event by email, fax or telephone, and shall provide detailed, written reports as soon as possible.

Information regarding serious adverse events will be transmitted to the sponsor using the Serious Adverse Event Form, which must be signed by a member of the investigational staff. The initial report of a serious adverse event may be made by email, and facsimile (fax). In addition, the SAE may also be forwarded to the TFDA by the sponsor within the appropriate time frame as follows:

If an adverse event results in death or is life-threatening, an SAE should be reported to TFDA within 7 days after becoming aware of the event, and shall provide detailed written documents within 15 days after awareness. If an adverse event results in hospitalization, prolonged hospitalization, disability/incapacity, is a congenital anomaly/birth defect, or requires medical and/or surgical intervention, an SAE should be reported to TFDA within 15 days and provide detailed written document after awareness. Any SAE should be reported promptly according to the reporting procedure of each IRB(s).

6.1.6. Managements of AE

The using of EpiFaith syringe will not change the managements of AEs.

Table 6. The managements of common AEs related the procedure of epidural localization.

AEs	Treatments
Post puncture headache	Supporting treatment such as rehydration, simple analgesics, opioids and anti-emetics may control the symptoms in milder cases. Generally, >85% of headaches after lumbar puncture will resolve without any specific treatment. Depending on the severity of the headache, prolonged hospital stay for better care and procedure such as blood patch may be required.
Accidental intravascular catheter placement	The intravascular catheter can either be withdrawn (1 cm at a time then flushed with saline and aspirated) until no more blood is be aspirated, or it can be totally removed and replaced.
Accidental subarachnoid catheter placement	The risk of inadvertently administering an epidural dose intrathecally. The headache may occur, and prolong hospital stay for better care and procedure such as blood patch may be required.
Bleed at needle entry area	Clean the puncture area with sterile protocol.

6.2. Data Safety Monitoring Plan

An Independent safety monitor (anesthesiologist) will call for terminating the study early if more than 5 subjects experience inadvertent dural puncture.

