1. INTRODUCTION

Locating the epidural space is an indispensable part of obstetrical analgesia, surgical anesthesia, postoperative analgesia, and chronic pain control.

The traditional method of locating the position of the needle tip is loss of resistance technique (i.e., the

"LOR"), which is based on detecting the pressure drop occurring at the moment the needle tip reaching the epidural space. Because the pressure of the epidural space is lower than the cavities of others tissue, a free injection of air or liquid from the syringe can be induced, resulting in a sudden loss of resistance of the plunger. Thus, the anesthesiologist can detect the pressure drop by feeling the resistance of pushing the plunger of the attached syringe.

The epidural space is a very thin area near the spinal cord. The advance of needle must be stopped right after the needle tip reaches the epidural space to prevent accidental dural puncture, which may lead to cerebrospinal fluid leakage followed by intractable headache and injuries of the spinal nerves. However, the current incidence rates of accidental dural punctures are 0.19-3.6%¹.

Using the LOR hand feeling to locate epidural space relies on manual skill of the operator and the considerable experiences. Choosing air or saline for LOR technique depends on personal experiences of the operator. The variety of LOR techniques has increased the difficulty of learning².

Some objective and confirmatory devices based on LOR technique are developed, such as Episure and Epidrum, and have been discuss under clinical trial³⁻⁵. The results show a lower failure rate and a shorter time needed to identify the epidural space. However, the restriction of the media and the actuating pressure selection will deprive the anesthesiologists' habit.

The EpiFaith syringe is an improved LOR device with the ability to warn and help physicians to achieve the safe insertion is required. EpiFaith syringe provides objective, and quantitative pressure information as well as a visual signal which is triggered at the moment the needle tip enters the epidural space. Hence, the anesthesiologist can get a clear endpoint for the advancing of the needle easily. The advantages of EpiFaith syringe including that the anesthesiologist can control the epidural needle with both hands and achieve the real- time pressure detection.

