3. STUDY DESIGN

3.1. Overall Study Design

This is a single blind, randomized study. Subjects who will receive a surgery requiring combined spinal -epidural technique and meet all of the study criteria will be enrolled in the study. All subjects must sign an informed consent and receive a copy of the signed and dated informed consent form prior to participation in the trial.

The study consists of 2 study visits: Visit 1 (Screening Visit) and Visit 2 (Operative Visit). After screening, eligible subject will be randomly assigned to one of the following groups: Group A: detection by EpiFaith syringe with air, or Group S: detection by EpiFaith syringe with saline with a 1:1 ratio. In Visit 2, the following variables will be recorded and rated during the process of epidural space localization: Success of epidural localization, time to identify the epidural space, duration of the epidural space localization procedure, number of attempts, Number of the occurrence of false positive, the distance from the skin to the epidural space, and number of change insertion segment. Adverse events and concomitant treatments will be also recorded.

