3.2. Study Population

3.2.1. Subject number

Recruitment will stop when approximately 60 subjects are included.

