7. STUDY ENDPOINTS

7.1. Primary Endpoint

• Success of epidural localization

(defined as the catheter can be inserted into epidural space successfully, no cold perception in the blocked dermatomes after the injection of anesthetic by cold sensation test, and no occurrence of inadvertent dural puncture.)

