8. STATISTICAL METHODS

8.1. Planned Sample Size

Considering the recommendation given by Lancaster, Dodd &Williamson. A total of 60 subjects (30 subjects per group) will be required in this study to obtain parameters such as ratio, mean and standard deviation which will be used in a sample size calculation for the full-scale trial, and to estimate the rate of participants who drop out of the trial.

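### Section 6.2 stops the trial only at the 6th dural puncture, pooled over arms and regardless of number treated, with no stated tolerable rate or operating characteristics, so it reacts slowly.

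*Combined protocol and SAP*

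**What the plan says.** Section 6.2 (Data Safety Monitoring Plan) is a single sentence: an independent safety monitor, an anesthesiologist, calls for an early end to the study "if more than 5 subjects experience inadvertent dural puncture". It gives no denominator, arm, review time, reference rate or rationale.

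Section 1 states that "the current incidence rates of accidental dural punctures are 0.19-3.6" per cent. That range appears only there, as motivation for the device, and 6.2 does not cite it.

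On size, Section 8.1 says "A total of 60 subjects (30 subjects per group) will be required in this study", and Section 3.2.1 says "Recruitment will stop when approximately 60 subjects are included". The two arms use the same syringe and differ in medium, air or saline, allocated 1:1 (Section 3.1). Section 7.1 makes "no occurrence of inadvertent dural puncture" part of the definition of success, so each puncture is also a primary-endpoint failure.

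Other safeguards exist but carry no number. Section 6.1.5.2 requires any SAE to be reported to the sponsor and the IRB. Section 9.4.2 lets the IRB, TFDA or other agencies discontinue the study at any time.

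**The concern.** Section 1 names accidental dural puncture as the harm to be avoided, with cerebrospinal fluid leakage, intractable headache and nerve injury as consequences. A fixed count with no denominator cannot respond to an early cluster: five punctures among the first 20 subjects leave it silent. A pooled count is also insensitive to an excess confined to one medium, although air versus saline is the randomized contrast. Since 6.2 states neither a rate to protect against nor the chance of stopping at any rate, neither the monitor nor an ethics committee can judge whether the rule protects subjects adequately. If it is followed as written, subjects may continue to be exposed after a run of events that background rates would rarely produce.

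**Working it through.** **Inputs.** Trigger: 6th subject with a puncture (6.2). Number treated: 60, 30 per arm (8.1). Reference rates: 0.19% and 3.6% (Section 1). Two and three times the upper rate are 2 × 3.6% = 7.2% and 3 × 3.6% = 10.8%. The rates 10% and 15% are assumed for illustration. Dropout is not given, since the trial is itself meant "to estimate the rate of participants who drop out of the trial"; 60 treated is assumed, with 54 to 66 as a range.

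**The plan's own figure.** The documents give no derivation of the threshold, so there is nothing to reproduce. At full enrolment it corresponds to 6/60 = 10% (exact 95% CI 3.8% to 20.5%). At subject 30 it corresponds to 6/30 = 20%.

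**Chance of ever firing.** A fixed count checked after every event has fired by subject n exactly when at least 6 of the n have had a puncture:

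P(fires by n) = 1 − Σ(k=0 to 5) C(n,k) p^k (1−p)^(n−k).

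At p = 0.108 and n = 60 the sum is 0.3595, so P = 0.6405.

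| True rate | Expected events in 60 | P(fires) | P(misses) |
|---|---|---|---|
| 0.19% | 0.11 | about 0 | – |
| 3.6% | 2.16 | 2.1% (false stop) | – |
| 7.2% | 4.32 | 26% | 74% |
| 10% | 6.0 | 56% | 44% |
| 10.8% | 6.48 | 64% | 36% |
| 15% | 9.0 | 90% | 10% |

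Sensitivity of the miss at 10.8% to number treated: 46.5% at 54, 36.0% at 60, 27.0% at 66.

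**Speed.** At 10.8% the same formula gives firing by subject 30, 40 and 50 with probability 9.8%, 26% and 46%. The mean number treated, given that the rule fires, is Σ(n=6 to 60) n C(n−1,5) p^6 (1−p)^(n−6) / P(fires). This is 47 at 7.2%, 44 at 10% and 37 at 15%.

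**Early cluster.** Five or more punctures in the first 20 subjects has probability 0.0006 at 3.6%. Exactly five would not trigger the rule.

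**Excess in one arm.** This uses the sum of Binomial(30, p1) and Binomial(30, 3.6%). With p1 = 15%, P(at least 6) = 49%. With p1 = 10.8% it is 26%.

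**Would indexing to number treated help?** This is illustration only, not a proposed threshold. At each n, take the smallest count x with P(X ≥ x | n, 3.6%) at or below a chosen pointwise tail, and compute stopping by exact recursion.

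| Rule | False stop at 3.6% | Fires at 10% | Mean treated at stopping, 10% |
|---|---|---|---|
| Present count | 2.1% | 56% | 44 |
| 1% tail, no ceiling | 2.8% | 51% | 29 |
| 0.5% tail, present count as ceiling | 2.9% | 58% | 36 |

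Without the ceiling, eventual detection falls (at 10.8%, 58% against 64%). With it, nothing is lost, because every trial that the present rule stops is still stopped, no later.

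The means in the table are conditional on stopping. Counting 60 for trials that run to the end, expected numbers treated at 10% are 0.56 × 44 + 0.44 × 60 = 51 for the present rule, and 0.58 × 36 + 0.42 × 60 = 46 for the rule with a ceiling.

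**Formal arm-level limits.** Adding a pointwise 1% limit within each arm raises the false-stop chance at 3.6% to about 5%. This comes from simulation with an assumed block size of 4; Section 3.4 gives no block size.

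**The case against.** The case for the present rule has four parts.

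First, it rarely stops an acceptable trial: 2.1% at the top of the background range. A termination threshold should lie above background, and the exact lower limit for 6/60, 3.8%, is just above 3.6%. This stands. A reader might infer that 6.2 conflicts with the 0.19-3.6% in Section 1. The documents do not support that: the range is background, the rule never cites it, and no section makes it a tolerable rate. What is missing is any stated link.

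Second, the rule is not blind to a large excess. A reader might infer that a threefold excess is missed about half the time. With the planned 60 it is 36%; it approaches half only with fewer treated (46.5% at 54) or if detection is required by subject 50.

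Third, the count is not the only safeguard. The text says when the monitor will call for termination, not that the monitor may not act earlier, and SAE reporting and regulatory powers remain. This stands too, so it cannot be said that the study can only be stopped late. But none of these supplies a numerical criterion, and 6.2 as written prompts no action before the 6th event.

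Fourth, pooling is partly defensible. Both arms use one device, and with 30 per arm any arm-level limit rests on very few events. Formal arm-level limits also carry a real false-stop cost. That argues for stricter arm-level limits or for review without a formal limit, not for leaving the arms unexamined.

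**Conclusion.** The point holds as one of unstated justification and slow response. The rule is workable at full enrolment and has a low false-stop chance. It misses a twofold excess over the upper background rate about 74% of the time and a threefold excess about 36%. At the threefold rate it has acted by mid-trial in only about 10% of trials. A one-arm excess of 15% against 3.6% goes undetected about half the time (fires 49%).

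These figures assume 60 treated, independent subjects with a constant rate in each arm, and a check after every event. They use 3.6% as a yardstick because it is the highest rate the documents quote, not because they call it acceptable. The amendment is worth making: it is cheap and concerns subject safety, but the present rule is not internally contradictory.

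**What to change.** Amend 6.2 as follows.

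- The sponsor and the safety monitor state the maximum tolerable rate and the reason for it, and say how it relates to the range in Section 1.
- Restate the rule as a table of cumulative punctures by number of subjects treated, checked after each event, with the present count kept as a ceiling so that eventual detection is not reduced.
- Have the monitor also review counts by arm. Any formal arm-level limits should be stricter than the pointwise 1% tail examined above; otherwise use arm counts for review only.
- Print the operating characteristics: the chance of stopping and the expected number treated at the tolerable rate and at two or three higher rates, including an excess in one arm only.

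The cost is one table and a short paragraph, with no extra subjects or staff. The downside to disclose is a slightly higher chance of an unnecessary stop (2.9% against 2.1% at 3.6% in the illustration), rising to about 5% if arm-level limits at a pointwise 1% tail are added. The tolerable rate and the thresholds remain the decision of the sponsor and the monitor.
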